4.2.1 Oral induction

The agreed oral three-year induction protocol, derived from the Dutch regimen of Bannink et al [23], together with a final (fourth) year, of maintenance treatment is shown in Table 2a. A 2-year protocol for older girls (e.g. aged >14 years) in whom a shorter induction period is desired by the clinician and family, is given in Table 2b

Dose is based on body weight and is recalculated at the beginning of each year.

 $17-\beta$ estradiol will be given in its micronized (e.g. Estrace) or hemihyrate (e.g. Cetura) form using 0.5 mg tablets which can be halved by the family.

Alternatives such as esters - $17-\beta$ estradiol valerate (e.g. Climaval and Zumenon) and hemihyrate preparations (e.g. Elleste solo and Estrofem) are acceptable but only available as 1 mg tablets so that participating centres would therefore need their pharmacy to prepare a suitable dose from a 1 mg tablet.

Girls receiving <0.25 mg daily with any preparation would also need their medication prepared by the pharmacist. Girls receiving <0.25 mg daily with any preparation will require their pharmacy to prepare the correct dose in capsule form, as currently practiced in The Netherlands using Cetura. (Documentation from Amalia Children's Hospital, Radboud University Medical Center, Nijmegen, available on request). In patients requiring ≥0.25 mg daily the dose will be rounded to the nearest 0.25 mg. Evening administration is recommended, to mirror the transdermal regimen.

Table 2a Three-year oral 17β -estradiol regimen for pubertal induction and, in italics, a suggested first post-induction year [21]. The dose is calculated according to body weight at the beginning of each year and given before sleep each night.

Year (months)	Dose of estradiol [microgram/kg/day]
1 (0-12)	5
2 (13-24)*	7.5
3 (25-30)	10
3 (31-36)	15
4 (37-48)**	20†

*Girls in whom low final height is anticipated or who are markedly short at the start of induction (defined as ≤3 standard deviations below the population mean) may be offered a slower induction by receiving an extra 6 months of 7.5 microgram/kg/day between Year 2 and Year 3. **Morning serum estradiol sample is recommended at the beginning of Year 4.

[†]This post-induction dose equates to about 1 mg daily. However, the dose required will vary between 1 and 4 mg daily, depending on patient sensitivity, most patients requiring at least 2 mg daily.

Table 2b Two-year oral 17β -estradiol regimen for pubertal induction in girls presenting late (e.g. >14 years) and judged by clinician and family to require a shorter induction period. Year 3 corresponds to post-induction dose. The dose is calculated according to body weight at the beginning of each year and given before sleep each night.

Year (months)	Dose of estradiol [microgram/kg/day]
1 (0-6)	5
1 (7-12)	7.5
2 (13-18)	10
2 (19-24)	15
3 (25-36)	20 [†]

Transdermal vs oral 17β-estradiol protocol Version 1.0 July 12th 2020

During the fourth year of maintenance treatment, estradiol dose will vary between 1-4 mg daily, depending on patient sensitivity, most patients requiring at least 2 mg daily.

4.2.2 Transdermal induction

Table 3 shows the agreed regimen, adapted from the Swedish protocol of Ankarberg-Lindgren [16] in which an overnight patch is applied for 10-12 hours during the first two years of induction. Dosage is weight-based and increased in accordance with weight at the clinic visit. Patches are applied on a healthy part of the skin (buttocks, belly or lower part of back), cutting the appropriate dose as described [21]. A new patch is applied on a different part of the skin. During the third year of induction the dose is split during the 24-hour period, cutting the desired patch piece in half to give two pieces, applying both pieces overnight then removing one in the morning. The stability at 21 and 35°C and uniformity of estradiol distribution has recently been demonstrated for Evorel, Estraderm and Oesclim (50µg, 50µg and 25µg per 24 hours) patches when cut into 8 pieces [24]. Therefore, while a new 25µg patch is normally required each day for older girls, those with a low body weight may receive a second piece during the next 24 hours.

Table 3a Three-year protocol for transdermal 17β - estradiol pubertal induction regimen and a suggested first post-induction year. The dose at the beginning of each year is calculated according to body weight.

	Weight (kg)	50 µg patch	25 µg patch	Duration of treatment, Instructions
Year 1*				
	< 40 kg	1/16 of patch (3.1 µg)	1/8 of patch (3.1 μg)	10-12 hours (overnight, to mimic the normal diurnal variation)
	40-55	1/12 of patch (4.2 μg)	1/6 of patch (4.2 μg)	
	>55	1/8 of patch (6.2 µg)	¼ patch (6.2 μg)	
Year 2				
	< 40 kg	1/8 of patch (6.2 µg)	1/4 of patch (6.2 μg)	10-12 hours (overnight)
	40-55	1/6 of patch (8.3 µg)	1/3 patch (8.3 μg)	
	>55	¼ of patch (12.5 µg)	½ patch (12.5 μg)	
Year 3				
	< 50 kg	1/3 of patch (16.7 μg)	2/3 of patch (16.7 μg)	Cut the desired dose into two halves; attach both parts to the skin in the evening.
	50-65	3/8 patch (18.8 μg)	3/4 patch (18.8 μg)	After 10-12 hours (overnight) remove one part, keep the second part during the day. Remove
	>65	1/2 of patch (25 µg)	1 patch (25 µg)	second part in the evening, before evening application of a two further half patches. This results in a diurnal dose variation, with higher dose nighttime.
Year 4**	Post-induction dose			
	Not applicable	50 – 75 (-100) μg/24h (Often ~1 ug/kg/24h)		Patch continuously attached to the skin. Apply whole patch three times weekly, changing after 2 days Serum sample for estradiol target to be drawn in the morning after the previous evening's
			· · · ·	dose, target range 150–450 pmol/L

*Girls in whom low final height is anticipated may receive an extra 6 months of the Year 1 dose **Year 4 suggests a post-induction dose

**Serum estradiol sample to be drawn early of Year 4 in the morning using the post-induction dose and a new patch applied the evening before, target range 150–450 pmol/L [25]

Table 3b Two-year transdermal 17β -estradiol regimen for pubertal induction in girls presenting late (e.g. >14 years) and judged by clinician and family to require a shorter induction period. Year 3 corresponds to suggested post-induction dose. The dose at the beginning of each year is calculated according to body weight.

	Weight (kg)	50 µg patch	25 µg patch	Duration of treatment,	
				Instructions	
Year 1 (0-	-6 months)				
	< 40 kg	1/16 of patch (3.1 µg)	1/8 of patch (3.1 µg)	10-12 hours (overnight, to mimic the normal diurnal variation)	
	40-55	1/12 of patch (4.2 μg)	1/6 of patch (4.2 μg)		
	>55	1/8 of patch (6.2 µg)	¼ patch (6.2 µg)		
Year 1 (7-	-12 months)				
	< 40 kg	1/8 of patch (6.2 μg)	1/4 of patch (6.2 µg)	10-12 hours (overnight)	
	40-55	1/6 of patch (8.3 µg)	1/3 patch (8.3 μg)		
	>55	¼ of patch (12.5 μg)	½ patch (12.5 µg)		
Year 2					
	< 50 kg	1/3 of patch (16.7 μg)	2/3 of patch (16.7 μg)	Cut the desired dose into two halves; attach both parts to the skin in the evening.	
	50-65	3/8 patch (18.8 µg)	3/4 patch (18.8 μg)	After 10-12 hours (overnight) remove one part keep the second part during the day. Remove	
	>65	1/2 of patch (25 µg)	1 patch (25 µg)	second part in the evening, before evening application of a two further half patches. This results in a diurnal dose variation, with higher dose nighttime.	
Year 3**	Post-inductio				
	Not applicable	50 – 75 (-100) μg/24h (Often ~1 ug/kg/24h)		Patch continuously attached to the skin. Apply whole patch three times weekly, changing after 2 days Serum sample for estradiol target to be drawn in the morning after the previous evening's	
Sirls in wh	hom low final h			dose, target range 150–450 pmol/L e an extra 6 months of the Year 1 dose	

*Girls in whom low final height is anticipated may receive an extra 6 months of the Year 1 dose **Year 4 suggests a post-induction dose

** Serum estradiol sample to be drawn early of Year 3 in the morning using the post-induction dose and a new patch applied the evening before, target range 150–450 pmol/L [25]

4.3 Oral progesterone administration

An oral progestogen such as Dydrogesterone (9β ,10 α -pregna-4,6-diene-3,20-dione) 10 mg; micronised progesterone 100 mg; and medroxyprogesterone acetate 5 mg initially [13] is recommended but depends on local availability. A duration of 10 days each calendar month is recommended, in keeping with the Cincinnati guidelines [13].

To allow maximum time for uterine and breast development with unopposed estrogen, pubertal staging and where possible pelvic ultrasound examination should be carried out at the time of first breakthrough bleeding-so that endometrial thickness and uterine size can be determined [21].

Depending on the assessment, a decision should be taken to either introduce progesterone, or delay doing so and review after 6 months (or earlier if breakthrough bleeding becomes problematic).

Features suggesting postponing progesterone treatment include: Tanner stage B3 breast development or less: uterine length < 5 cm, i.e. the 50th centile for general Scottish population aged 13 years [26], fundo-cervical ratio \leq 1 (i.e. infantile or cylindrical configuration) and endometrial thickness \leq 2 mm. Features suggesting that progesterone should be introduced include Tanner B4-5 development, uterine length \geq 5 cm, fundo-cervical ratio > 1 (pubertal or pear-shaped configuration) and endometrial thickness > 2 mm.

4.4 Concurrent treatment with growth hormone (GH) and oxandrolone

It is anticipated that most girls will be receiving both GH therapy at the time of pubertal induction and to continue this until around 16 years of age, or when height velocity is < 2 cm/year . Participating centres are likely to give standard GH doses for TS - 1.4 mg/m²/day, equivalent to 50–65 microgram/kg/day [26] and modified according to individual GH responsiveness. Insulin-like growth factor-1 (IGF-I) should be measured at the beginning of induction and then annually as per the Cincinnati guidelines [13], aiming for values between +1.5 and +2.5 SDS and modifying GH dosage to keep IGF-1 below +3 SDS.

The weak anabolic steroid Oxandrolone is not currently manufactured in Europe but is available although expensive to import from the United States of America and Australia. Consequently, although shown to improve adult height in TS in the dose of 0.05 mg/kg/day (maximum dose 2.5 mg daily) [27], Oxandrolone tends to be reserved for girls who respond poorly to GH despite good compliance [28].

No standard approach to either GH or Oxandrolone treatment can be imposed on participating centres, and variations in these treatment options will be factored into the data analysis.

4.5 Data collection before and during pubertal induction

Table 4 shows the recommended information to be collected before, during and at the end of pubertal induction, and until adult height, i.e. height velocity < 2 cm/year.

TABLE 4 Recommended measurements before, during and at the end of pubertal induction with either transdermal or oral 17-β
estradiol grouped according to priority – essential and desirable.

Variable	Before induction (± 6 months)		End of Years 1 & 2	End of Year 3	Comment	
ESSENTIAL	(2 o montho)	visito				
Karyotype	X				From time of diagnosis	
Auxology Height (cm)	x	x	x	х		
Weight (kg)	X	Х	X	Х	 Previous growth data will be requested, to enable calculation of a) height velocity, using 12 (±1) month interval, during previous year; and GH responsiveness – derived from height/weight status one year prior to, at the start of, and one year after starting GH. 	
Height velocity (cm/yr)	X		X	Х		
Measured parental heights (where available)	X					
Breast and pubic hair stage (1-5)	X	Х	X	Х		
Systolic & diastolic blood pressure (mm Hg)	Х	Х	Х	Х	Lowest of three consecutive readings using Dinamap V100 or similar device	
Adherence to treatment		X	Х	Х	Scored according to estrogen doses missed per month as good (≤ 2) moderate (≤ 4) and poor (> 4)	
Adverse events/illness		Х	Х	Х	All adverse events (e.g. injury, intercurrent infection) irrespective of relevance to growth and puberty	
FSH, LH	X			Х		
Free T4 and TSH	Х			Х		
Liver function	Х		Х	Х		
HbA1c	Х			Х		
Concurrent treatment	Х	Х	Х	Х	GH, L-T4, Oxandrolone	
DESIRABLE	1					
Final adult height					Measurement once height velocity < 2cm/year	
Bone age	Х		Х	Х	Assessed using 'BoneXpert', where available	
Sitting height	X	X	Х	Х		
Echocardiography	X			Х	Including measurement of aortic size index	
Pelvic ultrasound	Х		X	Х	Uterine length, shape and volume, endometrial thickness	
DXA BMC	Х			Х	Hip and lumbar spine z-score Total body BMD	
Fasting lipid profile	Х			Х	Cholesterol, triglycerides, low and high-density lipoproteins	
Coagulation studies	X			Х		
Serum estradiol	X			Х	Beginning of Year 4 (see Table 2)	
Serum IGF-I	X		Х	Х	Keep +1.5 -2.5 SD of reference range	
24h continuous ambulatory blood pressure	X			Х		
Fasting blood glucose and insulin	Х			Х		

Abbreviations

FSH = follicle stimulating hormone; LH = luteinising hormone; fT4 = free thyroxine; TSH = thyroid stimulating hormone; DXA = dual X-ray absorptiometry; BMC = bone mineral content; BMD = bone mineral density; GH = growth hormone; L-T4 = levo-thyroxine. *4-monthly visits are recommended; however 3-6 monthly may be more suitable for some participating centres.

It should be noted that measurements such as height, weight, pubertal stage and blood pressure are marked as 'essential' and are within the scope of any paediatric service caring for girls with TS. By contrast, 'desirable' measures should be undertaken at the clinician's discretion, and take account of the resources available in the participating centre.

Since height gain during induction is the agreed primary outcome measure, previous height and weight data from one year before, at the time of and one year after the start of GH treatment and at least yearly thereafter, together with GH dose and possible oxandrolone treatment, are required to assess GH responsiveness [29,30].

Karyotype (normally available from time of diagnosis) is essential information.

At each visit, measurement of height, weight, blood pressure, pubertal stage, adherence (scored according to the number of estrogen doses estimated by the family to have been missed per month), recording of adverse events, and concurrent treatment are required.

Note that the family will be asked at each visit about **any** adverse events including minor injury, intercurrent infection, middle ear problems and gastrointestinal symptoms, and summarised at the end of each year by the clinician.

Annual biochemistry for thyroid function and liver function, FSH, LH and estradiol levels will be carried out as part of normal clinical practice.

Echocardiogram to define the anatomy of the heart and great vessels, with measurement of aortic root diameter at the annulus, and aortic size index (aortic root diameter divided by body surface area), is recommended before and at the end of induction.

Pelvic ultrasound, measuring uterine length, fundo-cervical ratio, uterine shape (infantile, cylindrical and pubertal) and endometrial thickness are also recommended before and after induction.

Dual X-ray absorptiometry (DXA), with measurement of bone mineral density at the lumbar spine and hip is recommended before and at the end of induction, the measurements being converted to standard deviation scores. Due to different machines in different centres, with no possibility to harmonise the data from the range of equipment, the patients' individual change in bone mineral density standard deviation score will be the used variable in the study.

As stated above, these investigations depend on local availability and are not prerequisites for participation in the study.

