3.2 Outcomes

The primary outcome measure is height gain in cm during the pubertal induction period, since this can be accurately determined in the context of an international framework. Secondary outcome measures include final adult height, systolic blood pressure, aortic root diameter, uterine size and shape, bone mineral density, adherence and dropout rate.

Table 1 Outcome measures to be analysed at the end of pubertal induction in girls with Turner syndrome using either an oral (see Tables 2a and 2b) or transdermal (see Tables 3a and 3b) 17- β estradiol regimen approved by the Turner Syndrome Working Group of ESPE.

Induction period is normally 3 years (plus 6 months for very short girls), exceptionally 2 years for girls presenting late (e.g. >14 years), minimum follow up is during induction period but where possible, follow up is to final adult height.

Primary outcome measure

Pubertal height gain, i.e. increase in height in centimetres during the (usually) 3-year pubertal induction period

Secondary outcome measures

- Final adult height in centimetres & population-specific SDS
- Change in population-specific height SDS between start and end of pubertal induction
- Breast development (clinical assessment)
 - Tanner B4-5 reached
 - Satisfactory breast shape (ie not tubular, no overdevelopment of areolae) according to attending clinician (graded as satisfactory or unsatisfactory)
- Cardiovascular health
 - Systolic & diastolic blood pressure at the end of induction (lowest of three readings or mean values if recorded by ambulatory 24-hour blood pressure monitoring
 - Change in aortic root diameter and aortic size index between start and completion of induction
- Patient satisfaction; adherence/compliance with treatment
 - Percentage drop-outs from either regimen
 - Average of good, reasonable and poor rating with adherence during pubertal induction (3 years ± X months)
 - Patient satisfaction with shape and size of breast (scoring 1-5 where 5=best)
 - Patient satisfaction with mode of administration (scoring 1-5 where 5=best)
- Uterine health and sex hormone profile at the end of induction
 - Uterine length and volume, endometrial thickness
 - Uterine shape and fundo-cervical ratio
 - LH and FSH
 - Serum 17-β estradiol

- Skeletal age and bone health
 - Change in bone age/chronological age per year
 - Change in size-adjusted whole body lumbar spine and hip bone mineral areal density (BMAD) (z-score) before and after induction
- Metabolic profile

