6.2 Sample size

Mean (SD) height gain during three years of pubertal induction in the UK clinical trial of Gault et al [26] in which TS girls were treated with a consistent dose of GH has been calculated as 12.2 (3.5) cm. A mean difference of 2.5 cm between transdermal and oral regimens is considered clinically significant, giving a fractional effect size (f) of 2.5/3.5 = 0.71. Using the Lehr formula where $n=21/f^2$ gives the number of patients in each arm of the study required for 90% power at the 5% level [31], the number would be 42. However, given the covariates including age at diagnosis, karyotype, age at starting growth hormone therapy, differing dosage regimens, and use or not of Oxandrolone amongst the enrolled patients, a recruitment target of twice the power calculation, i.e. up to 84 in each treatment arm, is considered desirable so as to adjust for potential confounding factors. Note that this target of 84 in each treatment arm applies to girls undergoing the full 3-year induction period and does not include girls undergoing the shortened induction period.

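### Table 4 lets the start height of the primary outcome be taken up to 6 months from the start of estradiol; height needs its own narrow window

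*Protocol*

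**What the plan says.** Section 3.2, Table 1, defines the primary outcome as "Pubertal height gain, i.e. increase in height in centimetres during the (usually) 3-year pubertal induction period". It does not say which measurement counts as the start height.

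Section 4.5, Table 4, lists height as an essential measurement in a baseline column headed "Before induction (± 6 months". The same heading covers karyotype, blood tests, echocardiography, pelvic ultrasound and DXA. No footnote gives height a separate rule. On visit spacing, the table's footnote says "4-monthly visits are recommended; however 3-6 monthly may be more suitable for some participating centres". The end-of-induction column is labelled as the end of Year 3, with no tolerance.

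Section 4.1 describes an open study in which families and clinicians choose the route, partly according to which preparations are available locally. Section 4.6 lists start-of-induction height among the propensity-score variables, without a timing rule and without the measurement interval. Section 5 has data sent to the European centre at enrolment and at each year end.

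Section 6.2 gives the planning figures: mean (SD) gain over three years "has been calculated as 12.2 (3.5) cm", and "A mean difference of 2.5 cm between transdermal and oral regimens is considered clinically significant".

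**The concern.** A gain score carries any timing error in its first measurement straight into the outcome. A height taken months before the first dose adds pre-treatment growth to the gain. A height taken months after it removes part of the growth under study. Nothing in the protocol ties the start height to the first dose, scales the gain to the interval actually observed, or corrects for that interval.

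Randomisation would make timing error balance on average. Here route is chosen and depends partly on local supply, while visit spacing is left to each centre. Centre can therefore drive both route and measurement timing. If it does, a difference in clinic habit would appear as a difference between routes. Adjusting for start-of-induction height would not remove it, because that covariate is the same loosely timed value. A larger sample would not remove it either, since bias does not shrink with n.

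**Working it through.** **Inputs.** Mean gain 12.2 cm, SD 3.5 cm, target difference 2.5 cm, 90% power, 5% level, 42 per arm doubled to 84 (all section 6.2). Baseline window ±6 months (Table 4).

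**1. The plan's own figure.** Lehr: 21/(2.5/3.5)² = 41.2, or 21/0.71² = 41.7 with the rounded effect size. Both give 42. The two-sided normal formula also gives 42. The sample size is reproduced and is not in question.

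**2. Growth rate.** 12.2/3 = 4.07 cm/year, or 4.07/12 = 0.34 cm/month. This is a three-year average; the protocol gives no rate for the months around the start.

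**3. Shift for one girl.** 4.07 × 0.5 = 2.03 cm either way, which is 2.03/2.5 = 81% of the target difference. With assumed rates of 3, 5, 6 and 7 cm/year (not in the protocol), the 6-month shift is 1.5, 2.5, 3.0 and 3.5 cm.

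**4. Timing alike in both arms.** Assume timing is uniform over the full 12-month window and independent of the gain.

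- Added SD = 4.07/√12 = 1.17 cm
- Total SD = √(3.5² + 1.17²) = 3.69 cm

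| | SD 3.50 | SD 3.69 |
|---|---|---|
| n per arm for 90% power | 42 | 46 |
| Power at 42 per arm | 90.5% | 87.4% |
| Power at 84 per arm | 99.6% | 99.2% |

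At 84 per arm: SE = 3.5 × √(2/84) = 0.540, and Φ(2.5/0.540 − 1.96) = 0.996. With SD 3.69, SE = 0.569 and Φ(2.5/0.569 − 1.96) = 0.992.

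**5. Mean timing differs between arms.** False effect = 4.07 × months/12. The false-positive rate is for no true difference, 84 per arm, SD 3.5, two-sided 5%, normal approximation. The month values are assumptions, chosen to show the scale.

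| Difference in mean timing | False effect | Share of 2.5 cm | False-positive rate |
|---|---|---|---|
| 1 month | 0.34 cm | 14% | 10% |
| 2 months | 0.68 cm | 27% | 24% |
| 3 months | 1.02 cm | 41% | 47% |

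**6. After narrowing.** With a 1-month limit, the start height can be off by at most 0.34 cm (14% of 2.5 cm) at the average rate. A 1-month tolerance at the end adds at most another 0.34 cm.

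**The case against.** Several points on the other side have force.

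- **The outcome is already anchored.** Section 3.2 speaks of gain during induction and section 4.6 of height as induction begins. A height taken 6 months into treatment fits neither. This stands as evidence of intent, but Table 4 is the rule that sites will follow, and its heading says otherwise.
- **A start visit is likely.** Sections 4.2.1 and 4.2.2 base the dose on weight at the beginning of each year, and section 4.5 asks for height at each visit. A 6-month offset is therefore unlikely as routine. But nothing makes that visit's height the baseline, and visits may be 6 months apart.
- **The analysis plan can choose the baseline.** It can choose among recorded heights and correct for dates. It cannot recover a height that was never taken near the start, so the collection window belongs in the protocol.
- **The window was probably meant for scans and blood tests.** Quite possibly. As written it also governs height.

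A reader might also draw stronger conclusions that the protocol does not support. The two ends of the window are 4.07 cm apart, more than the 2.5 cm target, but that compares two individual girls at opposite extremes, whereas 2.5 cm is a difference between arm means. The unfilled tolerance "3 years ± X months" in Table 1 belongs to the adherence rating, so it does not show that the height window was left open. The request for "height velocity, using 12 (±1) month interval, during previous year" concerns the spacing of two past heights. It shows that the authors limited timing for another growth measure, but not that a 1-month window around the first dose is feasible everywhere.

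**Conclusion.** The point holds as a badly set measurement window for half of the primary endpoint, and it should be fixed. The heading contradicts itself, and it allows an individual's start height to move by up to 2.0 cm either way at the protocol's average growth rate.

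The effect on the trial result depends on a fact that the protocol does not give. If timing is alike in both arms, the loss is negligible at the actual target: 99.6% to 99.2% power. If mean timing differs, the bias is about 0.34 cm per month. The design makes such a difference possible, but nothing in the protocol shows that it will occur, its size or its direction. The 3-month figure of about 1.0 cm is illustrative. The concern therefore rests on avoidable bias, not on power, and it does not show that the planned comparison is invalid.

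**What to change.** In Table 4:

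- Give height its own baseline rule: the last height on or before the first estradiol dose, and within about 1 month of it.
- Take the end height within about 1 month of the end of the girl's own induction period (2, 3 or 3½ years). A single 36-month time point would not fit the 2-year and 3½-year inductions, and for the longer one would cut off the last 6 months of the outcome period.
- Record the exact dates of the first dose and of every height. Make sure that the data sent to the European centre under section 5 include the visit heights with their dates.
- Where a visit misses the window, interpolate to the required date from the adjacent visit heights.
- Keep the ±6 months for scans and blood tests only, and reconcile the word for before with the ± sign.

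The cost is a wording change in Table 4 and two or three date fields. Height is already essential at every visit. The small downside is that some girls will have an interpolated start or end height, which assumes steady growth between the two visits used.
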